## **2. OBJECTIVES AND ENDPOINTS**

### **2.1 Objectives**

#### **2.1.1 Primary Objective**

The primary objective of the study is to evaluate the effect of EDP-305 on ALP levels.

#### **2.1.2 Secondary Objectives**

The secondary objectives of the study are as follows:

- To evaluate the safety and tolerability of EDP-305
- To evaluate the effect of EDP-305 on bilirubin levels
- To evaluate the effects of EDP-305 on other markers of liver function
- To evaluate the effects of EDP-305 on non-invasive markers of liver fibrosis
- To evaluate the effects of EDP-305 on inflammatory markers
- To evaluate the effects of EDP-305 on lipids
- To evaluate the effects of EDP-305 on pruritus
- To evaluate the effects of EDP-305 on Quality of Life (QoL)
- To evaluate the PK of EDP-305 and metabolites in plasma
- To evaluate the PD of EDP-305

### **2.2 Endpoints**

#### **2.2.1 Primary Endpoints**

The primary endpoint of the study is the proportion of subjects with at least 20% reduction in ALP from pretreatment values or normalization of ALP at Week 12.

#### **2.2.2 Secondary Endpoints**

The secondary endpoints are as follows:

- Frequency of adverse events (AEs), serious AEs, and AEs leading to discontinuation through Week 12
- Bilirubin (Total, Conjugated, Unconjugated) decline from Baseline at Week 12
- Change from Baseline in Alanine aminotransferase (ALT) and Aspartate aminotransferase (AST), Gamma-Glutamyl transferase (GGT) at Week 12
- Change from Baseline of noninvasive liver fibrosis markers (Enhanced Liver Fibrosis [ELF] panel, PRO C3, AST to Platelet Ratio Index [APRI] and fibrosis-4 [FIB-4]) at Week 12

- Change from Baseline in fibrinogen, CRP, IL6, IL1 $\beta$ , TNF- $\alpha$ , TNF- $\beta$ , alpha2 macroglobulin and haptoglobin levels at Week 12
- Change from Baseline in Triglycerides (TG), Total Cholesterol (TC), High Density Lipoprotein Cholesterol (HDL-C), Low Density Lipoprotein Cholesterol (LDL-C) at Week 12
- Change from Baseline in 5D-itch scale and Visual Analog Score (VAS) at Week 12
- Change from Baseline in PBC-40 Quality of Life (QoL) at Week 12
- Pharmacokinetic parameters of EDP-305 (and metabolites):  $C_{max}$ ,  $T_{max}$ , and  $AUC_{last}$
- Pharmacodynamic parameters of EDP-305: FGF19, C4, and Bile Acid (BA) at Week 12

### 3. SELECTION OF SUBJECTS

A total of approximately 119 subjects with a diagnosis of PBC are planned for enrollment into this study.

#### 3.1 Subject Inclusion Criteria

Each subject must meet all of the following criteria to be enrolled into this study:

1. An informed consent document must be signed and dated by the subject
2. Male and female subjects of any ethnic origin between the ages of 18 and 75 years, inclusive
3. Male or female with a diagnosis of PBC by at least two of the following criteria:
  - History of ALP above ULN for at least 6 months
  - Positive Anti-Mitochondrial Antibodies (AMA) titers ( $>1/40$  on immunofluorescence or M2 positive by enzyme linked immunosorbent assay [ELISA] or positive PBC-specific antinuclear antibodies [PBC-ANAb])
  - Documented liver biopsy result consistent with PBC (with no cirrhosis)
4. For subjects with no documented liver biopsy performed within 2 years, subjects must undergo a transient elastography (Fibroscan) showing liver stiffness  $<14.0$  kPA
5. Must be on a stable dose of UDCA 12-20 mg/kg/day for at least 6 months prior to Screening or intolerant of UDCA in the opinion of the Investigator (no UDCA for at least 12 weeks prior to Screening)
6. Alkaline Phosphatase (ALP)  $\geq 1.67 \times$  ULN and/or total bilirubin  $>ULN$  but  $<2 \times$  ULN ( $<2.4$  mg/dL)
7. Subjects must have Screening laboratory values for Hepatitis B surface antigen (HBsAg), anti-HCV antibodies and HCV RNA negative, and Human Immunodeficiency Virus (HIV) 1 and 2 antibodies (Ab) as seronegative. NOTE: Subjects previously infected by chronic hepatitis C and treated with direct acting antivirals (DAAs) with sustained virologic response (SVR) for at least 3 years will be allowed.
8. Female subjects of childbearing potential must agree to use two effective methods of contraception from the date of Screening until 90 days after the last dose of EDP-305. Effective methods of contraception are defined as:
  - a condom for the male partner and at least one of the following for the female participant:
    - Intrauterine device
    - Oral, injectable, implantable, transdermal, or intravaginal hormonal contraceptiveNote: The above does not apply to female subjects of non-childbearing potential (ie, physiologically incapable of becoming pregnant) defined as:
  - has had a complete hysterectomy greater than or equal to 3 months prior to dosing or
  - has had a bilateral oophorectomy (ovariectomy) or
  - has had a bilateral tubal ligation or fallopian tube inserts or

- is postmenopausal (a demonstration of a total cessation of menses for  $\geq 1$  year with an FSH level of  $>35$  mIU/mL).
9. All male participants who have not had a vasectomy must use effective contraception from Day -1 to 90 days after their last dose of study drug. Effective contraception is defined as a condom and spermicide for the male, or condom and at least one of the following for a female partner:
    - Intrauterine device
    - Oral, injectable, implantable, transdermal, or intravaginal hormonal contraceptive
    - Be of non-childbearing potential
  10. Male subjects must agree to refrain from sperm donation from the date of Screening until 90 days after their last dose of study drug
  11. Screening body mass index (BMI) of  $\geq 18$  kg/m^2
  12. Subject must be willing and able to adhere to the assessments, visit schedule, prohibitions and restrictions, as described in this protocol

### 3.2 Subject Exclusion Criteria

Subjects who meet any of the following criteria will be excluded from this study:

1. Laboratory Screening Results:
  - AST  $>5 \times$  ULN
  - ALT  $>5 \times$  ULN
  - Patients with Gilbert's syndrome will not be allowed due to interpretability of bilirubin levels
  - Total white blood cells (WBC)  $<3000$  cells/mm^3
  - Absolute neutrophil count (ANC)  $<1500$  cells/mm^3
  - Platelet count  $<140,000$ /mm^3
  - Prothrombin time (international normalized ratio, INR)  $>1.2$
  - Serum creatinine  $>2$  mg/dL or clearance creatinine  $<60$  mL/min (based on Cockcroft-Gault Method)
2. Suspected to have relevant nonalcoholic fatty liver disease (NAFLD) as based on the judgment of the Investigator at Screening
3. Known history of alpha-1-Antitrypsin deficiency
4. Use of immunosuppressants known to have an effect on the liver of patients with PBC (eg, colchicine, methotrexate, or azathioprine) in the 3 months preceding Screening.
5. Current use of fibrates, including fenofibrates. NOTE: Subjects who discontinued fibrates for at least 3 months before Screening can participate
6. Use of an experimental treatment for PBC within the past 6 months
7. Prior use and/or concomitant treatment with OCA
8. Use of experimental or unapproved drugs within 1 year of Screening

9. Any other condition(s) that would compromise the safety of the subject or compromise the quality of the clinical study, as judged by the Principal Investigator (PI)
10. Pregnant or nursing females
11. Recipients of liver or other organ transplantation or anticipated need for orthotropic organ transplantation in one year as determined by a Model for End-Stage Liver Disease (MELD) Score  $\geq 15$
12. Co-existing liver or biliary diseases, such as primary sclerosing cholangitis, choledocholithiasis, acute or chronic hepatitis, autoimmune hepatitis, alcoholic liver disease, nonalcoholic steatohepatitis (NASH), acute infection of bile duct system or gall bladder, history of gastrointestinal bleeding (secondary to portal hypertension), cirrhosis, cholangiocarcinoma diagnosed or suspected liver cancers
13. Cirrhosis with or without complications, including history or presence of: spontaneous bacterial peritonitis, hepatocellular carcinoma
14. Hepatorenal syndrome (type I or II) or Screening serum creatinine  $>2$  mg/dL (178  $\mu$ mol/L)
15. Prior variceal hemorrhage, uncontrolled encephalopathy, Child-Pugh Class A, B and C, esophageal varices, or refractory ascites within the previous 6 months of Screening (defined as date informed consent signed)
16. Patients with a history of severe pruritus requiring current or prior systemic treatment (e.g., with BAS or rifampicin)
17. Medical conditions that may cause non-hepatic increases in ALP (e.g., Paget's disease)
18. Any condition possibly affecting drug absorption (eg, gastrectomy  $<3$  years prior to Screening). NOTE: Subjects who have undergone gastric surgeries known to not affect drug absorption such as gastric band or gastric sleeve will be allowed if they are stable for at least 1 year prior to Screening.
19. History of regular alcohol consumption exceeding 14 drinks/week for females and 21 drinks/week for males within 6 months of Screening. One drink is defined as 5 ounces (150 mL) of wine or 12 ounces (360 mL) of beer or 1.5 ounces (45 mL) of hard liquor)
20. Participation in a clinical trial within 30 days prior to study drug administration
21. Clinically significant electrocardiogram (ECG) abnormalities or QTcF greater than 450 ms for males and 470 ms for females at either Screening or Baseline, or any prior history of QT abnormality
22. Use of CYP3A4 and P-gp inducers and inhibitors within 14 days prior to the first dose of study medication and throughout study duration
23. Clinically significant history of drug sensitivity or allergy, as determined by the PI
24. Subject has received an investigational agent or investigational vaccine within 30 days, or a biological product within 3 months or 5 elimination half-lives (whichever is longer) prior to the planned intake of study drug
25. Use of a new statin regimen from Screening and throughout study duration.  
NOTE: Subjects on a stable dose of statins for at least 3 months prior to Screening are allowed. No dose modification during the study will be allowed.
26. Use of immunosuppressants (eg, systemic corticosteroids) for more than 2 consecutive weeks in duration within 1 year prior to Screening.

## 4. STUDY DESIGN

This is a Phase 2, randomized, double-blind, placebo-controlled, dose-ranging study assessing the safety, tolerability, pharmacokinetics, and efficacy of two doses of EDP-305 in subjects with PBC with or without an inadequate response to UDCA.

[figure not shown]
The study is composed of 3 phases or periods:

- Screening period which includes the Screening Visit and may occur over a time period of 28 days prior to the first dose of study drug
- Treatment period which begins with the first dose of study drug on Day 1 and concludes with the End of Treatment (EOT) Visit on Day 84 (Week12)
- Safety Follow-up period which includes the End of Study (EOS) Visit on Day 112.

### 4.1 Dose and Treatment Schedule

Subjects will be randomized in a 3:3:1 ratio to one of two doses of EDP-305 and placebo. Every subject will receive a single daily dose of blinded study drug for a total of 12 weeks. An overview of the study design is shown in Figure 1. Study visits and assessments are detailed in the Schedule of Assessment (SoA) in Appendix 1.

**Figure 1: Study Design**

Abbreviations: D=Day; W=Week

## 4.2 Rationale for Study Design

This proposed trial will evaluate EDP-305 in patients with PBC who will be randomized to one of three treatment groups: (1) 1 mg EDP-305, (2) 2.5 mg EDP-305, or (3) placebo in a 3:3:1 ratio.

### 4.2.1 Justification of Design and Control Group

Until recently, ursodeoxycholic acid (UDCA) has been the only approved treatment for PBC, which was approved by the FDA in 1997. While UDCA therapy has a marked impact on clinical outcomes in PBC, up to 40% of UDCA-treated patients have a suboptimal or absent response to UDCA and, as such, are at significantly increased risk of an adverse outcome (death, requiring a liver transplant, or other clinical complications) (*Carbone et al., 2013; Corpechot et al., 2008; ter Borg et al., 2006*) (U.S. Department of HHS Organ Procurement and Transplantation Network.) (<https://optn.transplant.hrsa.gov>, Sept 5, 2016). In May 2016, the U.S. Food and Drug Administration granted accelerated approval for the FXR agonist Ocaliva® (obeticholic acid, OCA) for the treatment of PBC in combination with UDCA in adults with an inadequate response to UDCA, or as a single therapy in adults unable to tolerate UDCA (U.S. Food and Drug Administration, 2016). The confirmatory trials are ongoing.

This Phase 2 double-blind, parallel dose group study evaluating 3 doses of EDP-305 compared to placebo was designed to assess the safety, efficacy, and PK of EDP-305 for the treatment of subjects with PBC over a 12-week treatment period. This trial will establish the effect of adding EDP-305 to the PBC standard of care treatment, UDCA on the ALP change. Patients will continue their pre-study stable dose of UDCA throughout the trial. Accordingly, patients will not have any standard therapies withheld in the trial. The use of placebo is implemented to maintain the study blind and scientific validity of the trial. Some patients cannot tolerate UDCA; their standard of care does not include UDCA. Patients taking drugs that might have effects in PBC or recently conditionally approved (i.e., OCA) are being excluded from the trial to ensure that the trial provides the clearest comparison of the effects of EDP-305 with placebo.

### 4.2.2 Justification of EDP-305 Dose

This phase 2 trial has been designed to assess the efficacy, safety and tolerability of 2 doses (1 mg, and 2.5 mg) of EDP-305 in patients with PBC so as to provide proof of concept data to support Phase 3 in this indication.

Study EDP 305-001 characterized a broad range of single and multiple doses: from 1 to 80 mg in the SAD part, and from 0.5 to 20 mg in the MAD part, and administered as an oral suspension. The safety and tolerability of EDP-305 has been established not only in healthy subjects but also in subjects with presumptive NAFLD at doses up to 80 mg single dose and up to 20 mg once daily for 14 consecutive days.

As demonstrated in study EDP 305-001, EDP-305 was generally well tolerated at single doses up to 80 mg and at multiple doses up to 20 mg for 14 days. No SAEs or Grade 4 AEs were reported. No clinically significant laboratories were reported except one transient Grade 2 ALT/AST elevation in n=1 (MAD-HV-20mg) that led to drug discontinuation. Drug related pruritus was reported after multiple dosing at the higher doses of EDP-305 10 mg (n=2) and 20 mg (n=7), and PBO (n=1), with 1 discontinuation at 20 mg in HV. Total, LDL-, HDL- cholesterol and triglycerides did not differ between EDP-305 and placebo in healthy at any dose or PN subjects at any dose, except for cholesterol and HDL at 20mg.

The pharmacokinetics of EDP-305 was profiled over a broad range of single and multiple doses. A dose proportional increase in exposure was observed over the broad dose range studied. Half-life ranged from 11-16 hours and from 10-23 hours following single and multiple doses of EDP-305, respectively. There was more drug accumulation observed following 20 mg dose compared to lower doses, indicating a potential change in the PK profile at 20 mg.

[REDACTED]

Based on observed safety profile to date, pharmacokinetics profile and changes in C4 and FGF-19 in study EDP 305-001 and relative bioavailability data from study 006, (Section 1.4.2.4), EDP-305 doses of 1 and 2.5 mg once daily using the tablet formulation are selected for this study. The exposures associated with this dose range are expected to result in clinically meaningful changes in C4 and other relevant markers of FXR activity (FGF-19), while minimizing the incidence of potential adverse events (i.e. pruritus).

[REDACTED]

[REDACTED] Doses of 1 and 2.5 mg using the tablet formulation in the fasted state (comparable to approximately 2.5 and 5 mg using the suspension formulation in the fasted state)

are expected to provide exposures associated with clinically meaningful changes in C4 and FGF-19, while minimizing the incidence of potential adverse events (i.e. pruritus).

In summary, based on data from studies 001, 004, and 006, doses of 1 and 2.5 mg are expected to provide:

- A safe and tolerable regimen with lowest chance to induce pruritus
- Plasma exposures representing linear, time-independent PK and correlated with desirable dose dependent changes in PD markers suitable for a once daily dosing
- Maximal decreases in C4 ranging from approximately 67% to 85% at steady state and associated increases in FGF-19 ranging from approximately 1000% to 1700% at steady state. Given the similarity in the MOA between EDP-305 and OCA, the expected changes in C4/FGF-19 over the selected dose range for EDP-305 in phase 2 studies, are expected to be associated with relevant downstream pharmacological effects clinically relevant changes in liver markers.

## 5. STUDY DRUG AND TREATMENT OF SUBJECTS

### 5.1 Description of Study Drug

EDP-305 drug product tablets consist of 1 mg, and 2.5 mg strengths supplied as round, white to off-white tablets debossed with I, and II respectively, to differentiate strength on one side of the tablet. Matching placebos for the two strengths will also be supplied as round, white to off-white tablets debossed with I, and II for 1mg, and 2.5 mg strengths respectively. Study drug and matching placebo tablets will be supplied by Enanta.

The matching placebo will contain all the excipients present in the EDP-305 drug product tablets with the exception of the active drug. [REDACTED]

[REDACTED]

[REDACTED]

[REDACTED]

EDP-305 drug product tablets and matching placebo tablets should be stored under refrigerated conditions (2°C – 8°C) at all times.

Additional information will be provided in the Pharmacy Manual.

### 5.2 Packaging and Labeling

EDP-305 tablets and matching placebo will be supplied in [REDACTED]

[REDACTED] All bottles containing clinical trial material will be labeled according to study drug labeling in compliance with applicable local and national regulations for labeling of investigational products.

EDP-305 tablets are packaged in a [REDACTED]

[REDACTED] The bottles will be induction sealed.

### 5.3 Storage

EDP-305 drug product tablets and placebo tablets in bottles will be shipped to the clinical site and stored under refrigerated conditions (2°C–8°C).

### 5.4 Accountability

Study drug may be dispensed only under the supervision of the Investigator or authorized designee and only to study subjects. The Pharmacist or designated study staff will maintain

adequate records of 1) study drug received, 2) study drug dispensed to the subjects, and 3) drug returned by the subjects. Subjects will be instructed to return all used and unused study drug to the site. All used and unused study drug will be retained at the site according to instructions provided by Enanta or designee until monitored by the study monitor. The study monitor will review study drug records and inventory throughout the study.

## **5.5 Handling and Disposal**

Study drug must not be used for any purpose other than for administration to subjects enrolled into this clinical study. All study drug bottles that are opened and returned by subjects as well as those that are not opened or assigned to subjects will be retained at the site according to instructions provided by Enanta or designee until monitored by the study monitor. Full accountability of all study drug distributed to subjects will be documented per Section 5.4.

At the end of the study, Enanta will provide instructions for the destruction of any unused study drug. If Enanta authorizes destruction at the study site, the Investigator must ensure that the materials are destroyed in compliance with applicable environmental regulations, institutional policy and any special instructions provided by Enanta, and, that the destruction was adequately documented.

## **5.6 Treatment Assignment and Randomization**

Subjects will be randomized to study treatment using an Integrated Web Response System (IWRS). Subjects will be stratified initially by participation in the PK/PD substudy and then by a) prior use of fibrates and b) prior and/or current use of UDCA. Subjects will be randomized to the treatment groups shown below:

- Treatment Group 1 (N=45); EDP-305 1 mg orally for 12 weeks
- Treatment Group 2 (N=45); EDP-305 2.5 mg orally for 12 weeks
- Treatment Group 3 (N=15); Placebo (PBO) orally for 12 weeks

A minimum of 10 subjects per treatment group will be included in the PK/PD substudy. The randomization code will be produced by Enanta (or designee). The Enanta unblinded biostatistician or designee will review and approve the final randomization list.

During the Screening Period, subjects will be identified by a unique screening number assigned by the clinical site. Subjects who have completed screening assessments and are eligible for participation in the study will be randomized before the first dose of study drug (Day -1 or Day 1) and assigned a unique subject number which will be used to identify the subject throughout the study.

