### 7.2.1 Withdrawal Criteria

The primary consideration in any determination to discontinue a subject's participation must be the health and welfare of the subject. Reasons for withdrawal may include, but are not limited, to the following:

- Adverse Event
- Noncompliance with study drug dosing or study procedures
- Lack of efficacy
- Lost to follow-up
- Withdrawal by subject
- Protocol deviation

- Pregnancy
- Sponsor's decision to terminate the study
- Other

Subject-specific stopping rules due to AEs and/or laboratory abnormalities are outlined in Section 10.1.

Subjects who prematurely withdraw from the study for any reason after having been randomized will not be replaced.

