### 11.2 Sample Size Considerations

The planned sample size is approximately 105 subjects. Group sample sizes of 45 in each active arm and 15 in the placebo arm achieve 83.552% power to detect a ratio of the group proportions of 40%. The proportion in the smallest active arm is assumed to be 0.4000 under the null hypothesis and 0.0400 under the alternative hypothesis. The proportion in the placebo arm is 10%. The test statistic used is the two-sided Mantel-Haenszel test. The significance level of the test is 0.05. To account for a 10% discontinuation rate, 14 additional subjects will be enrolled to attempt to have 105 who complete treatment, bringing the total number of subjects enrolled to 119.

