## **11.5 Efficacy Endpoints**

### **11.5.1 Primary Efficacy Endpoints**

The primary efficacy endpoint of the study is the proportion of subjects with at least 20% reduction in ALP from pre-treatment values or normalization of ALP at Week 12. The denominator will be the number of subjects in the efficacy population (missing=failure). Treatment comparisons will be made using a Mantel-Haenszel test comparing each of the active treatment arms to placebo, separately.

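### Protocol 5.6 prints the completer target (45/45/15, 105 in all) as the randomised arm sizes, although the plan is to randomise about 119, which is about 51/51/17 at 3:3:1

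*Protocol*

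**What the plan says.** Protocol 5.6 introduces its list with "Subjects will be randomized to the treatment groups shown below" and then gives three sizes: "Treatment Group 1 (N=45); EDP-305 1 mg orally for 12 weeks", "Treatment Group 2 (N=45); EDP-305 2.5 mg orally for 12 weeks" and "Treatment Group 3 (N=15); Placebo (PBO) orally for 12 weeks". It does not call these completers, evaluable subjects or approximate numbers.

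Protocol 11.2 uses the same sizes for power: "Group sample sizes of 45 in each active arm and 15 in the placebo arm achieve 83.552% power". It then adds an allowance for 10% discontinuation: "14 additional subjects will be enrolled to attempt to have 105 who complete treatment, bringing the total number of subjects enrolled to 119". The synopsis and SAP section 5 repeat this text.

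Three other provisions fix how the numbers relate:

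- Protocol 9.2.1 treats enrolled subjects as randomised subjects.
- Protocol 7.2.1 states "Subjects who prematurely withdraw from the study for any reason after having been randomized will not be replaced".
- Protocol 11.5.1 and SAP 9.1.1 keep every dosed subject in the denominator of the primary endpoint and count a missing result as a failure.

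No section gives arm sizes for 119. SAP section 5 lists the three groups at 3:3:1 without sizes.

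**The concern.** The only arm sizes attached to randomisation are those meant to be left after dropout. The two readings that would reconcile them are closed off. Enrolled cannot mean screened, because 9.2.1 equates it with randomised. Replacement cannot bridge 105 to 119, because 7.2.1 excludes it.

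The 14 additional subjects exist to offset discontinuation. If someone took 5.6 as the randomisation target, that offset would disappear. Discontinuations would come out of the 105, those without a Week 12 ALP would count as non-responders, and placebo, already the smallest arm, would have 15 subjects rather than 17.

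**Working it through.** **Inputs.** Arm sizes 45/45/15 (Protocol 5.6 and 11.2); 105 completers, 119 enrolled and 10% discontinuation (11.2); ratio 3:3:1 (4.1); two-sided Mantel-Haenszel test at 0.05 (11.2); missing counted as failure (11.5.1).

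**Arm sizes.**

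- 45 + 45 + 15 = 105.
- 105 / 0.9 = 116.7. The next multiple of 7 is 119.
- 119 × 3/7 = 51 and 119 × 1/7 = 17, so 51/51/17.
- Expected completers from that split: 51 × 0.9 = 45.9 and 17 × 0.9 = 15.3, which matches the 45 and 15 of the power statement.

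**Power formula**, per comparison and unstratified:

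- p̄ = (n₁p₁ + n₂p₂)/(n₁ + n₂)
- SE₀ = √[p̄(1 − p̄)(1/n₁ + 1/n₂)]
- SE₁ = √[p₁(1 − p₁)/n₁ + p₂(1 − p₂)/n₂]
- power = Φ[(|p₁ − p₂| − 1.96·SE₀)/SE₁]

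The Mantel-Haenszel form multiplies SE₀ by √[N/(N − 1)]. The exact figures enumerate both binomials and add up the probability that the Mantel-Haenszel chi-square exceeds 3.84.

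**The plan's own figure first (45 vs 15, no dropout).** The stated power is 83.552%.

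- 40% vs the printed 10% placebo rate: p̄ = 0.325, SE₀ = 0.1396, SE₁ = 0.1065, power 59.8% (Mantel-Haenszel form 58.9%, exact 62.7%). The stated figure is not reproduced.
- 40% vs 4%: p̄ = 0.310, SE₀ = 0.1379, SE₁ = 0.0888, power 84.4% (83.8%, 87.5%). This is close to the stated figure, but it uses 0.04 for placebo, whereas the text attaches 0.0400 to the active arm.

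Which rates lie behind 83.552% is a separate question, so both are carried forward.

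**Effect of the arm sizes.** Assume 10% discontinue in each arm and all count as failures. The rates become 0.9 × 40% = 36% on active, and 0.9 × 4% = 3.6% or 0.9 × 10% = 9% on placebo. Both designs are diluted in the same way.

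| Rates | Method | 51 vs 17 | 45 vs 15 | Difference |
|---|---|---|---|---|
| 36% vs 3.6% | pooled normal | 83.2% | 76.4% | 6.8 |
| 36% vs 3.6% | Mantel-Haenszel normal | 82.6% | 75.6% | 7.0 |
| 36% vs 3.6% | exact | 87.0% | 81.4% | 5.6 |
| 36% vs 9% | pooled normal | 58.3% | 51.6% | 6.7 |
| 36% vs 9% | Mantel-Haenszel normal | 57.6% | 50.7% | 6.9 |
| 36% vs 9% | exact | 60.9% | 55.2% | 5.7 |

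Worked example, 36% vs 3.6%, pooled, with p̄ = 0.279 in both designs:

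- 51 vs 17: (0.324 − 1.96 × 0.1256)/0.0810 = 0.96, so Φ = 83.2%.
- 45 vs 15: (0.324 − 1.96 × 0.1337)/0.0862 = 0.72, so Φ = 76.4%.

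**The case against.** The best defence is that nothing in the plan sets out to randomise 105. Enrolment of 119 appears twice in the synopsis, in Protocol section 3, in 11.2 and twice in SAP section 5. Section 5.6 states no total and no cap, so a power loss requires one list to override six statements. This stands, and it makes the loss conditional.

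A reader might infer that 5.6 sets the limits in the randomisation system, so that 105 would in fact be randomised. The documents do not support that. Neither document mentions arm limits or says that the list is sized from 5.6. SAP section 5 reports that the schedule had already been generated and given to the system vendor, and it shows the groups without sizes.

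A reader might also put the loss at 8 points. That compares a diluted 45 vs 15 (76.4%) with an undiluted 45 vs 15 (84.4%). The missing-as-failure rule dilutes the 119-subject design too, so part of that gap does not come from 5.6.

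Counting all of the 10% as failures is also an upper bound. The 10% refers to discontinuation, not to missing ALP. Protocol 7.1.4 asks early discontinuers to attend an end-of-treatment visit, and the Week 12 window in SAP 6.3 opens at Day 71, so late discontinuers may still have a usable value.

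Lastly, an unpooled-variance formula gives a smaller difference, for example 79.8% vs 74.7% at 36% vs 9%. It is not the planned test.

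What the defence does not remove is the contradiction itself: 5.6 says randomised, and 11.2 uses the same numbers as the completer target.

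**Conclusion.** The point holds as an internal inconsistency in a sample-size figure. The sizes in Protocol 5.6 do not fit the plan to randomise about 119 subjects without replacement; 3:3:1 gives about 51/51/17.

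If 5.6 were followed, power per comparison would be about 5.6 to 7 points lower than with 119 randomised. That range rests on equal 10% discontinuation in each arm, every discontinuation counted as a failure, an unstratified test, and 40% response on active with 4% or 10% on placebo before dilution. The difference is nearly the same under either placebo rate. The power level is not: about 76% to 87% with 4%, and about 51% to 61% with 10%.

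**What to change.** In Protocol 5.6, either replace 45, 45 and 15 with approximately 51, 51 and 17 (total approximately 119), or keep the present numbers and label them as expected completers. The word approximately is needed because enrolment is itself approximate and randomisation is stratified. Confirm that the randomisation list already generated covers 119 subjects.

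The cost is one line of text and one check. No subjects are added, because 119 is already the planned enrolment.
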